Safety planning is a brief, ED-feasible intervention which has been demonstrated to save lives,^{4,5} and has been universally recommended by every recent expert consensus panel on suicide prevention strategies.^{3,6-8} In one popular version of the safety plan developed by Stanley et al,⁴ the patient is encouraged to write out the following items: identifying personal signs of a crisis; helpful internal coping strategies; social contacts or settings which may distract from a crisis; using family members or friends for help when in crisis; mental health professionals who can be contacted when in crisis; and restricting access to lethal means.⁴ In most emergency departments, safety-planning is done by clinical personnel such as psychologists or social workers, but these providers are often too busy to perform safety-planning well or have multiple other patient care responsibilities.

This project aims to answer the following three research questions: (1) Will ED patients with suicidal ideation/attempt accept coaching on safety planning from non-clinical personnel; (2) Are these safety plans of high-enough quality for clinical personnel; and finally, (3) Will ED patients with suicidal ideation/attempt complete safety plans electronically?

Please note that the study will not otherwise alter usual & customary care in the emergency department.

Concerns about peer vulnerability to relapse

[figure not shown]
Anecdotally, there have been concerns that peer-delivered interventions may not be effective in the ED, since peers may be vulnerable to relapse in the stress of the acute-care environment. As some authors have noted, working in acute care is stressful for many individuals, not just peers.⁹ However, it is not true that peers are too “fragile” for a study of this type. Findings from peers in non-ED environments have generally indicated that peers receive positive benefit from the experience,¹⁰ including increased confidence and self-esteem.¹¹ Nonetheless, peers will be given the opportunity to experience the ED environment before committing to this project (please see “Recruitment of peers for this project” and “Training of peers” below). In addition, peers will be closely monitored and debriefed by the sub-investigator of this project ([name]), who is a licensed clinical counselor (please also see “Supervision and debriefing of peers” below). While

Title: Written safety planning vs the Safety Net app: A prospective randomized pilot trial
PI: [name], PhD
Site: University of Arkansas for Medical Sciences

adverse events are not expected as a result of this intervention, the PI will carefully monitor for any such event and report any adverse event to the IRB. In addition, if a peer has a relapse or any psychiatric emergency during the course of the intervention, they may contact [name] using the contact information provided during peer training. After this initial contact, [name] will debrief the peer by meeting with them and further discussing the situation.

Please note that although peers will receive mandatory confidentiality training required at the study institution, there is little concern that peers will “say the wrong thing” or break a patient’s confidentiality. Given that these peers have personal experience of hospitalization, it is more likely that they will be willing to guard the patient’s confidentiality and less likely than clinical staff to make insensitive remarks to a patient. However, all peers will be CITI-certified, with periodic reminders about patient confidentiality from the investigators.

Figure 1: Suicide safety planning training cycle

Description of interventions

Written safety plan: Please see separate upload for the Stanley et al version of the safety plan. This safety plan contains 6 components, and is completed by the patient themselves. This intervention takes approximately 20-40 minutes to complete. As a former site for the ED-SAFE study,¹² the UAMS ED typically has patients complete safety plans if being discharged. This is typically done by the psychiatric nurse or social worker if they are available, and this individual then places a progress note in the electronic medical record (EMR). These clinical providers must approve all safety plans in this study as peer support specialists and other research staff do not have the ability to place notes in the EMR.

Stanley-Brown Safety Plan app (i.e., Safety Net app): The Safety Net app is an electronic version of a safety plan and it is available for download in Apple’s App Store. A preview of this app is available at: <https://apps.apple.com/us/app/stanley-brown-safety-plan/id695122998>. This app is owned by Two Penguins Studios, LLC. It was developed in partnership with the New York State Office of Mental Health. Unlike the paper version, the Safety Net app allows participants to email a copy of their safety plan to whomever they wish. It also allows patients to dial 911 or the National Suicide Prevention Lifeline from the app.

Please see Figure 2 below for study flow. The app only stores deidentified data locally on UAMS secured tablets. Thus, the safety plan will have to be shown or emailed to clinical staff in order to be entered into the electronic medical record. Please note that peers and other research staff do not have the ability to place notes in the EMR.

[figure not shown]

Figure 2. Study flow.

Study Design and Procedures

This is an effectiveness-implementation randomized controlled trial which will be conducted in the emergency department (ED) at the University of Arkansas for Medical Sciences (UAMS) in Little Rock, Arkansas. The UAMS ED is an urban emergency department which sees approximately 60,000 patients per year, including more than 1,200 suicidal patients.

This clinical trial will compare the intervention of ED patients completing an electronic safety plan with a peer or other research staff member to completing a traditional written safety plan with a peer or other research staff member. Patients triaged and flagged with the chief complaint of "SI", "suicidal ideation", "suicide attempt", or "Psychiatric BEE" on the ED trackboard when a peer or other research staff member is available will be approached to participate. Patients will be approached after evaluation by an emergency physician.

Study flow: Utilizing trained nonclinical staff (i.e., peers or other research staff directed by the investigator team), staff will approach patients identified from the ED trackboard as being at risk for suicide until as many as 30 patients have been enrolled. Please see Figure 2 above for study flow. Patients are typically triaged by UAMS nursing staff as being "at-risk" after questions about self-harm. If so triaged, patients are then flagged with the chief complaint "SI", "suicidal ideation", "suicide attempt", or "Psychiatric BEE" on the ED trackboard and placed in a special area of the ED for evaluation. A partial waiver of HIPAA for recruitment purposes is requested to allow peers and other research staff to visualize the ED trackboard, and is appropriate for the following reasons:

- The PHI use or disclosure involves no more than minimal risk to the privacy of individuals based on the fact that no PHI will be recorded, reused, or

Title: Written safety planning vs the Safety Net app: A prospective randomized pilot trial

PI: [name], PhD

Site: University of Arkansas for Medical Sciences

disclosed to any other person or entity except as required by law or for authorized oversight of the research study.

- The research could not practicably be conducted without the requested waiver or alteration, as it would be difficult or impossible to identify ED patients at risk of self-harm in any other manner.
- The research could not practicably be conducted without access to and use of the PHI.

The trained peers and other research staff are UAMS nonclinical staff members who are participating in ED clinical research and who have received extensive training in safety planning (see below), data collection techniques, how to operate REDCap data collection software, and how to obtain informed consent. All are CITI certified and receive periodic reminders about confidentiality.

Upon approach by peers or other research staff, patients will be asked if they would like to participate in the study and if they would allow peers or other research staff to help them with safety planning. If the answer to both questions is yes, patients will be offered a brief screening procedure:

Inclusion criteria

- Presenting to the UAMS ED for suicidal ideation (SI) or after suicide attempt;
- Willingness to engage in safety planning with trained non-clinical staff;
- Have not already filled out a safety plan at the current visit

Exclusion criteria

- Prospective participants <18-years or >89-years of age;
- Presently incarcerated or in police custody;
- Non-English speaking;
- Critically-ill;
- Intoxicated with alcohol or other substances;
- ED staff objected against entering room;
- Unwilling or unable to complete the safety plan electronically;
- Unwilling or unable to use a tablet;
- Unwilling or unable to show/email this safety plan to clinical and research staff.

Title: Written safety planning vs the Safety Net app: A prospective randomized pilot trial

PI: [name], PhD

Site: University of Arkansas for Medical Sciences

If participants indicate interest in the study and meet all inclusion/exclusion criteria, informed consent will be obtained using IRB-approved consent forms & processes. If they provide consent, participants (n=30) will be randomized in a 1:1 fashion to either the traditional written safety plan group, in which they will complete a written safety plan with a peer support specialist or other research staff member, or the electronic "Safety Net" safety plan group, in which they will complete an electronic safety plan with a peer support specialist or other research staff member (please see Figure 2 above).

Participants will be randomized using the randomization function in REDCap. All participants will be allowed to complete the safety plan in the privacy of their ED treatment room. Please note that participants will be given a \$25 gift card for participating regardless of which group they are randomized into for the study.

After completing the safety planning process, participants will then be asked to answer a short questionnaire concerning their demographics (e.g., age, biological sex), any history of previous suicidal ideation, suicide attempts, or related behaviors, and satisfaction with the safety planning process.

Regardless of whether the safety plan is completed in the traditional paper format or electronically, this will be shown to the UAMS ED psychiatric registered nurse or social worker for approval and entry into the EMR. Please note that the study will not otherwise modify care in the ED. It is possible, although not likely, that psychiatry consultants could choose to revise, edit, or otherwise start anew with safety planning for a particular patient. If so, the patient will be withdrawn from the study.

Other measures: All participants will complete a brief questionnaire regarding their demographics, history of suicidal behaviors, and satisfaction with the safety planning process. After the visit, the electronic medical record will be searched for the following data: date/time of ED triage and disposition; length of ED stay; ED chief complaint or reason for visit; patient disposition (observation/admission/discharge/transfer); psychiatric diagnoses; and frequency of ED visits 3 months before and after the intervention. Length of ED stay will be compared against two control groups (obtained using AR-CDR): a) length of stay of all ED patients during a similar time period; and b) length of stay of ED patients who presented for SI during a similar time period. No PHI will be recorded for either of these deidentified control groups. Peers and other research staff will also be asked to record the total amount of time that they spent performing the safety plan intervention.

Study retention: The study duration is limited to the ED visit (typically <6 hours for SI patients), with participation in the study limited to the interventions mentioned above. Consequently, no special measures designed to increase retention are planned.

Title: Written safety planning vs the Safety Net app: A prospective randomized pilot trial
PI: [name], PhD
Site: University of Arkansas for Medical Sciences

Recruitment of peers for this project

Peers will be recruited through existing relationships with community suicide prevention organizations (i.e., Arkansas Foundation for Suicide Prevention, Arkansas Governor's Suicide Prevention Council, Veterans Service Organizations, etc.). Eligible recruits will complete an interview with [name] where they will be informed about the responsibilities and expectations of working with this project. Training and supervision of peers and other research staff will be used to further monitor the appropriateness of the individual to assist patients in providing the intervention.

Training of peers and other nonclinical individuals

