As a licensed clinical counselor, [name] will assess the provider's skill level and will become the role of a teacher, counselor, or consultant based on need. In other words, peers and mental health staffs will be provided with either instruction and direct feedback (i.e., the teacher role), support for reflection and processing of personal experiences (i.e., the counselor role), or encouraging confidence in required skills (i.e., the counselor role) depending on need.

In terms of direct supervision, [name] will be on site during the first week of the intervention to observe performance and operation. She will ensure that the safety plan is being administered, documented, and managed appropriately by each provider (see also "Fidelity of the intervention" below). If deficits are identified, she will work with individuals to make needed improvements. During the first week of intervention implementation, [name] will also conduct an individual face-to-face interview with each peer. Interview questions will be guided by the Consolidated Framework for Implementation Research (CFIR)¹⁹ and focus on identifying and overcoming perceived barriers to implementation of the intervention.

Peers will also be provided with clear instructions on how to obtain help during any difficult or uncomfortable situations during the intervention. After the first week of the intervention, peers may inform ED clinical staff (social worker or psychiatric nurse) on site of such situations so that the staff may continue working on the safety plan with the participant. ED clinical staff are available 24/7 so peers would not have much trouble in finding and asking someone for help with a participant during these situations. Participants who do not complete the safety planning with a peer will be withdrawn from the study, but peers will be informed that their safety and well-being remains a priority when completing the intervention and so they should not hesitate to ask clinical staff for help. Peers may also contact [name] using the contact information provided during

Title: Written safety planning vs the Safety Net app: A prospective randomized pilot trial
PI: [name], PhD
Site: University of Arkansas for Medical Sciences

peer training in order to schedule an in-person meeting. [name] will debrief the peer at these meetings by further discussing the difficult or uncomfortable situations.

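### Research question 3, on electronic completion, has no named outcome, and as the visible text reads, electronic uptake among otherwise eligible patients can only be bounded

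*Combined protocol and SAP*

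**What the plan says.** The introduction of the combined protocol and SAP lists three research questions. The last is "3) Will ED patients with suicidal ideation/attempt complete safety plans electronically".

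Under Study flow, a patient is asked about joining the study and about accepting help from non-clinical staff. "If the answer to both questions is yes, patients will be offered a brief screening procedure". The Exclusion criteria then remove anyone who is "Unwilling or unable to complete the safety plan electronically", "Unwilling or unable to use a tablet" or "Unwilling or unable to show/email this safety plan to clinical and research staff". Consent and 1:1 randomisation of 30 participants follow. On allocation the text says: "Participants will be randomized using the randomization function in REDCap".

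Data Analysis names four outcomes:
- Outcome 1: the proportion of approached patients who accept non-clinical help.
- Outcome 2: the proportion of approached patients who meet every criterion.
- Outcome 3: plan quality, with a count of plans redone.
- Outcome 4: satisfaction with each method.

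The Outcome measures paragraph adds that nothing further is to be recorded about a patient found ineligible. The section on measuring safety plan quality rates each plan section for completeness from 0 to 2, with a maximum of 16. Supervision and debriefing of peers states: "Participants who do not complete the safety planning with a peer will be withdrawn from the study".

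**The concern.** Question 1 corresponds to Outcome 1 and question 2 to Outcome 3. Question 3 corresponds to nothing.

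Patients who would answer no to question 3 leave at screening, where they are merged with exclusions for age, custody, language, critical illness, intoxication and the rest. If reasons are not tallied at that moment they cannot be reconstructed, because nothing else is kept on these patients. A reader of the results could not tell whether the electronic format suits nearly everyone otherwise eligible or only about half of them. For a pilot whose first two outcomes are acceptance and eligibility proportions, that is a relevant gap.

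**Working it through.** **Inputs from the documents.** Planned enrolment is 30 and at most 100 patients may be approached (Power calculations and sample size). Allocation is 1:1, so 30/2 = 15 per arm. If all 100 are approached, 30 enrolled is a yield of 30/100 = 30%. The completeness maximum reproduces: six steps with step 3 split in two, plus the section on what is worth living for, make 8 sections, and 8 × 2 = 16. There is no formal sample size and no target uptake rate to reproduce.

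**Assumed counts.** The documents do not give the number screened, the number eligible, the number excluded for electronic reasons or the number completing. All values below are illustrations.

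**Uptake among the screened and otherwise eligible.** Let S be the number who say yes to both questions and are screened, N the number meeting all criteria, and E the number failing only the two electronic criteria (electronic completion, tablet use).

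- Uptake = N/(N + E).
- Since E can be anything from 0 to S − N, uptake lies between N/S and 100%.
- Let R be those refusing only to show or email the plan, which may be a privacy matter. Uptake becomes (N + R)/(N + R + E) with R + E ≤ S − N. The minimum is at R = 0, so the bound is unchanged.

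Lower bounds:

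| S | N | N/S |
|---|---|---|
| 40 | 30 | 75.0% |
| 60 | 30 | 50.0% |
| 60 | 40 | 66.7% |
| 80 | 30 | 37.5% |
| 80 | 40 | 50.0% |

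N may exceed 30 because consent is sought after eligibility is established.

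**What a tally would give.** Take S = 60, N = 30 and 100 approached. Outcome 2 is 30% (exact 95% CI 21.2 to 40.0) whatever E is, yet:

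- E = 0: 30/30 = 100% (88.4 to 100)
- E = 10: 30/40 = 75.0% (58.8 to 87.3)
- E = 30: 30/60 = 50.0% (36.8 to 63.2)

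**S is not a named outcome either.** Outcome 1 counts agreement to coaching only. If 60 agree to coaching but 45 also agree to the study, the bound given S is 30/45 = 66.7%. Outcomes 1 and 2 alone support only 30/60 = 50%.

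**Completion in the app arm.** This can be obtained from the allocation and the completeness ratings. With all 15 randomised as denominator (exact 95% CI):

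- 15/15 = 100%, lower limit 0.025^(1/15) = 78.2%
- 14/15 = 93.3% (68.1 to 99.8)
- 12/15 = 80.0% (51.9 to 95.7)

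The denominator matters because non-completers are withdrawn. If three withdrawn participants were dropped, 12/15 would become 12/12 = 100%.

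**The case against.** **Completion is already measurable.** Question 3 read literally asks about completion, and both the allocation and a completeness scale exist. This stands. A reader might infer that the trial yields no estimate at all for question 3, and the documents do not support that. What they lack is a named outcome and a denominator wider than patients pre-selected as willing and able.

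**Figure 2 is not shown, and the recording rule may concern only patient-level data.** Both points stand in part. A reader might infer that counts by reason will certainly not be kept, but that cannot be established from the visible text. Read literally, however, the rule bars such a count, and at best it is unclear.

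**The exclusions might seem to bias the trial.** They do not bias the randomised comparison of quality and satisfaction. They apply before allocation and to both arms, and anyone randomised must be able to receive either format.

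**The 50% figure is extreme.** It requires 30 eligible out of 60 screened and every screen failure to be for electronic reasons alone. With 40 eligible the bound is 66.7%. It is a bound and not a forecast.

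**Redone plans are already tracked.** Outcome 3 counts them, which partly covers the case where "psychiatry consultants could choose to revise, edit, or otherwise start anew with safety planning for a particular patient". No new measure is needed for that.

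**The gain is limited.** Reluctance about the electronic format may also surface earlier, as refusal to join. A tally therefore describes the screened group and not all ED patients with suicidal ideation or attempt, and its interval will be wide.

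**Conclusion.** The point holds in a limited form. Question 3 has no named outcome. The computable completion figure rests on about 15 patients already screened as willing and able. In the visible text, exclusions for electronic reasons appear only within pooled Outcome 2, so uptake among the screened and otherwise eligible is known only to lie between N/S and 100%. The interval closes only if everyone screened is eligible. Its width in any example rests on assumed counts, and the conclusion is subject to what Figure 2 may contain. Severity is modest: the randomised comparison is unaffected, but the missing counts cannot be recovered afterwards and are cheap to collect.

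**What to change.** 1. Keep all criteria for randomisation. At screening, apply the two electronic criteria (electronic completion, tablet use) after the other criteria, and the show/email criterion last, so that a failure is attributable.
2. Amend the recording rule under Outcome measures to allow expressly an anonymous count, without identifiers, of patients who said yes to both questions, of those failing only the electronic criteria, and of those refusing only to show or email.
3. Name a question 3 outcome with exact 95% confidence intervals:
   - (a) Willing and able to plan electronically, divided by all screened and otherwise eligible. Report it as uptake in that group, not in all ED patients with suicidal ideation or attempt.
   - (b) Electronic plans completed, divided by all randomised to the app. Define completion in advance on the existing completeness scale, and count participants withdrawn before finishing as not completed.

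The cost is one extra screening tally and a minor IRB wording amendment. No patients, staff or protected health information are added.

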Title: Written safety planning vs the Safety Net app: A prospective randomized pilot trial
PI: [name], PhD
Site: University of Arkansas for Medical Sciences

once the study is complete. If so, electronic records will be audited to ensure high fidelity with the originals. These electronic copies will also be maintained on secure password-protected UAMS servers. When eventually destroyed, copies will be shredded per UAMS disposal guidelines.

Data collection will be performed through the Research Electronic Data Capture (REDCap) system on a secured UAMS wireless network, and it will be set up in cooperation with the UAMS Translational Research Institute (TRI) in order to assure 21 CFR Part 11 and HIPAA compliance.

Data Analysis

Outcome measures: Number of patients approached who agree to allow trained non-clinical staff to assist them with safety planning (if they do not agree, no other information about the patient will be recorded); the number of patients approached who meet all inclusion/exclusion criteria (if patients are not eligible for the study, no other information about the patient will be recorded); the number of participant safety plans which must be redone either by the peer support specialist, other nonclinical individuals, or clinical staff; the quality of completed safety plans; and patient satisfaction with each method.

Outcome 1: Evaluate the proportion of SI patients approached in the UAMS ED who agree to allow trained non-clinical staff to assist with safety planning. This number is currently unknown.

Outcome 2: Evaluate the proportion of patients approached who meet all inclusion/exclusion criteria. This number may be lower than the number of patients willing to participate in safety planning.

Outcome 3: Evaluate the quality of the completed safety plans. This will be done by retrospective review after the patient has left the ED. The number of safety plans that must be repeated or redone by clinical providers will also be tracked.

Outcome 4: Patient satisfaction with each method. This will be assessed by having the patient rate their experience with the safety planning process on a 7-point Likert scale (*strongly disagree; disagree; moderately disagree; neutral; moderately agree; agree; strongly agree*).

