Power calculations and sample size: As this is a pilot study, no formal sample size calculation is planned. The investigators plan a priori to enroll 30 patients. The investigators therefore ask for permission to approach a maximum of 100 patients.

Initially, the randomization scheme will be validated by comparing the groups on key variables that could be associated with outcome (e.g., age, biological sex, prior suicide

Title: Written safety planning vs the Safety Net app: A prospective randomized pilot trial

PI: [name], PhD

Site: University of Arkansas for Medical Sciences

attempts, prior completion of safety plan). Where we identify significant differences between groups, we will either adjust for these variables in analysis or conduct stratified analyses. Categorical variables will be analyzed with chi-square. Continuous variables will be analyzed by ANOVAs. Sub-analyses of potential prognosticators, including biological variables such as sex, will be descriptively presented, as the sample size will not likely permit sufficient testing of these variables.

Ethical Considerations

Written consent will be required for any study procedures. (please see “consent form.”). Please note that all study procedures will be conducted in accordance with all applicable government regulations and University of Arkansas for Medical Sciences research policies and procedures. This protocol and any amendments will be submitted and approved by the UAMS Institutional Review Board (IRB) to conduct the study.

Potential participants will be identified from the ED track board and/or patient triage note. This requires a partial waiver of HIPAA for recruitment purposes only. No PHI will be recorded or disclosed without patient consent. Please see study flow above.

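### Eligibility screens for fitness to use the app or tablet but not the handwritten plan, so the randomised population is selected for one format and app refusals go uncounted

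*Combined protocol and SAP*

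**What the plan says.** The Combined protocol and SAP lists nine exclusions under Exclusion criteria. Two concern the electronic format alone: "Unwilling or unable to complete the safety plan electronically" and "Unwilling or unable to use a tablet". A third, "Unwilling or unable to show/email this safety plan to clinical and research staff", is mainly about the app, although a paper plan must also be shown to clinical staff. The other six concern age, custody, language, critical illness, intoxication and objection by ED staff.

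The only willingness item under Inclusion criteria is "Willingness to engage in safety planning with trained non-clinical staff". It concerns who helps, not which format is used.

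Of the written plan, Description of interventions says: "This safety plan contains 6 components, and is completed by the patient themselves". No scribe or other accommodation is described.

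After screening and consent, "participants (n=30) will be randomized in a 1:1 fashion". Outcome 3 is the quality of the completed plans. The list of outcome measures also includes "patient satisfaction with each method", which is Outcome 4 and is rated on a 7-point scale. The same section says that nothing more is kept about a patient found ineligible.

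**The concern.** A randomised comparison of two formats normally enrols people who could take either one. Here a candidate who can write but cannot or will not use a tablet never enters. A candidate who can use a tablet but has trouble handwriting a six-part plan meets every criterion and has an even chance of being assigned to paper. The selection runs one way.

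Two things are at stake. First, the app-versus-paper contrast in Outcomes 3 and 4 describes a population already chosen for the app. A reader may take it as a statement about suicidal ED patients in general. Second, the third research question in the introduction asks whether such patients will complete plans electronically. Those who would answer no are removed at screening and merged into a single count of ineligible patients, so the trial cannot report them.

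**Working it through.** **1. Criteria set side by side.** Each inclusion and exclusion item was read for a format requirement.

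- Electronic completion: excluded if unwilling or unable.
- Tablet use: excluded if unwilling or unable.
- Showing or emailing the plan: mainly electronic, partly common to both formats.
- Handwritten completion: no item.

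**2. Arm size.** 30 patients at 1:1 gives 30/2 = 15 per arm. There is no design calculation to reproduce: "As this is a pilot study, no formal sample size calculation is planned". The documents give no rate of inability or refusal for either format, and no standard deviation. Everything in steps 3 and 4 is therefore an illustration on assumed values.

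**3. Direction of any tilt.** Suppose the formats do not differ among patients who can use both. Let a share *a* of candidates be app-unfit and a separate share *b* be paper-unfit, each scoring *D* Likert points lower on the unsuitable format. The app-minus-paper difference in mean satisfaction is then:

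- all comers: (b − a) × D, which is 0 when a = b;
- eligibility for both formats required: 0;
- the plan's one-sided rule: b/(1 − a) × D, which is always positive.

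With *a* and *b* each between 5% and 20% and *D* between 1 and 3:

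- lowest: 0.05/0.95 × 1 = 0.05;
- middle (a = b = 10%, D = 2): 0.10/0.90 × 2 = 0.22;
- highest: 0.20/0.80 × 3 = 0.75.

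The sign follows from the rule. The size follows only from the assumptions. These values also ignore consent, staff help and withdrawal, so the upper end is not a realistic estimate.

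**4. Chance that it arises at all.** If a share *p* of enrolled patients cannot or will not handwrite a plan, the chance of at least one among 15 paper patients is 1 − (1 − p)^15, and the expected number is 15p.

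| p (assumed) | Chance of at least one | Expected number |
|---|---|---|
| 2% | 26% | 0.3 |
| 5% | 54% | 0.75 |
| 10% | 79% | 1.5 |
| 20% | 96% | 3.0 |

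At 15 per arm, the difference detectable with 80% power at two-sided 5% is √(2/15) × (1.96 + 0.84) = 1.02 SD. A tilt would therefore matter mainly for the point estimates, which are what a pilot reports.

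**5. What happens to a paper patient who cannot finish.** Supervision and debriefing of peers says that participants who do not complete the plan with a peer are withdrawn. Such a patient would then contribute no score. One loss is 1/15 = 6.7% of the arm. The mean of those who remain is not pulled down. The effect becomes unequal loss after randomisation, falling on paper.

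**6. Research question 3.** App-unwilling candidates are removed before randomisation, and only the number eligible is kept. If all 15 app patients complete their plans, the trial shows 15/15 however many candidates declined the app at screening. Outcome 2 does not recover the refusals, because they share one count with the six exclusions that have nothing to do with format.

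**The case against.** The case on the other side has real force.

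- **Exchangeability.** Eligibility precedes randomisation, so the comparison is valid for the patients enrolled. Within that population, difficulty with handwriting is a genuine feature of paper. This stands.
- **Consent.** A patient who flatly refuses paper can decline 1:1 randomisation, and the consent form must be signed by hand. Both are partial screens. Consent filters app refusers equally, and a signature does not show ability to handwrite a plan that the protocol expects to take 20 to 40 minutes.
- **Help.** Patients in both arms complete the plan with trained staff, who coach their answers. No scribe is described, but none is ruled out, so a blank paper plan is unlikely. This stands.
- **Preference.** A reader might infer that the app arm cannot contain anyone who dislikes its format. The exclusions cover unwillingness and inability, not dislike. A reluctant but willing tablet user still enters.
- **Usual practice.** Written plans are typical at this site for patients being discharged, so screening only for the newer format is understandable. That explains the app criterion but does not supply the missing counterpart.

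A reader might also infer a specific bias: one paper patient scoring 0 would lower the arm's overall mean by up to 40/15 = 2.7 of 40 points. The documents do not support that figure. A true non-completer would more likely be withdrawn than scored 0. A zero also fits only total inability, whereas an assumed frequency of about one such patient would have to include people who would merely rather not write.

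**Conclusion.** The point holds as a one-way selection of the randomised population, together with a gap in what is recorded. No criterion mirrors the electronic-format exclusions for the handwritten plan. Any resulting tilt in Outcomes 3 and 4 would favour the app, and any differential withdrawal would fall on the paper arm.

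A reader might go further and call the allocation biased. The documents do not support this, because screening and consent come before randomisation and apply alike to both arms.

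The size cannot be derived from the documents and is probably small. The Likert and probability figures in the working rest wholly on assumed rates and show direction and plausibility only. The loss of refusals for research question 3 needs no such assumption: it follows directly from the exclusion and the recording rule.

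**What to change.** Reword the criterion to exclude anyone unwilling or unable to complete the safety plan in either study format (handwritten or on a tablet), making clear that failing one format is enough. Ask both halves at screening, before randomisation.

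Keep anonymous aggregate counts of exclusions by format reason, paper and electronic separately. Amend the outcome-measures text in Data Analysis, which now allows nothing further to be recorded on ineligible patients. The electronic count then supplies the refusals that research question 3 lacks.

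If the one-sided rule is kept, state that the between-format conclusions apply only to tablet-able, app-willing patients.

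The cost is one extra screening question, a small amendment and possibly a slightly lower Outcome 2 proportion. The two-format rule also leaves out patients who struggle with handwriting and might gain from the app; the counts would show how many.
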